#### *Evaluation of Non-Target Lesions*

Complete Response (CR): Disappearance of all non-target lesions and normalization of tumor marker level. All lymph nodes must be non-pathological in size (< 10 mm short axis).

Incomplete Response/Stable Disease (SD): Persistence of one or more non-target lesions and/or maintenance of tumor marker level above the normal limits.

Progressive Disease (PD): Appearance of one or more new lesions\* (new lesions must be > slice thickness) and/or unequivocal progression of existing non-target lesions.

Overall level of substantial worsening that merits discontinuation of therapy. A useful test that can be applied when assessing non-targets for unequivocal progression is to consider if the increase in overall disease burden based on the change in non-measurable disease is comparable in magnitude to the increase that would be required to declare PD for measurable disease.

Unknown (UN): Assessment of non-target lesions cannot be made due to insufficient or unevaluable data. In this case, a concise explanation must be given.

**\*Definition of New Lesion:** The finding of a new lesion should be unequivocal (i.e. not due to difference in scanning technique, imaging modality, or findings thought to represent something other than tumor (ex: new bone lesions may be healing or flare of pre-existing lesions). However, a lesion identified on a follow-up scan in an anatomical location that was not scanned at baseline is considered new and will indicate PD. If a new lesion is equivocal (because of small size, etc.), follow-up evaluation will clarify if it truly represents new disease and if PD is confirmed, progression should be declared using the date of the initial scan on which the lesion was discovered.

### ***Evaluation of Best Overall Response***

The best overall response is the best response recorded from the start of the treatment until disease progression/recurrence (taking as reference for progressive disease the smallest measurements recorded since the treatment started). The participant's best response assignment will depend on the achievement of both measurement and confirmation criteria.

### **For Participants with Measurable Disease (i.e., Target Disease)**

Target Lesions	Non-Target Lesions	New Lesions	Overall Response	Best Overall Response for when Confirmation is Required:
CR	CR	No	CR	$\geq 4$ wks confirmation
CR	Non-CR/Non-PD	No	PR	$\geq 4$ wks confirmation
CR	Not evaluated	No	PR	$\geq 4$ wks confirmation
PR	Non-CR/Non-PD/Not evaluated	No	PR	
SD	Non-CR/Non-PD/Not evaluated	No	SD	Documented at least once $\geq 4$ wks from baseline
PD	Any	Yes or No	PD	No prior SD, PR or CR
Any	PD*	Yes or No	PD	
Any	Any	Yes	PD	

\* In exceptional circumstances, unequivocal progression in non-target lesions may be accepted as disease progression.

Note: Participants with a global deterioration of health status requiring discontinuation of treatment without objective evidence of disease progression at that time should be reported as "*symptomatic deterioration*". Every effort should be made to document the objective progression even after discontinuation of treatment.

#### **9.1.4 Duration of Response**

Duration of overall response: The duration of overall response is measured from the time measurement criteria are met for CR or PR (whichever is first recorded) until the first date that recurrence or PD is objectively documented, taking as reference for PD the smallest measurements recorded since the treatment started.

Duration of overall complete response: The duration of overall CR is measured from the time measurement criteria are first met for CR until the first date that recurrent disease is objectively documented.

Duration of stable disease: Stable disease is measured from the start of the treatment until the criteria for progression are met, taking as reference the smallest measurements recorded since the treatment started.

#### **9.1.5 Progression-Free Survival**

Progression-Free Survival (PFS) is defined as the duration of time from study entry to time of objective disease progression.

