### **1.5 Secondary Endpoints**

- Disease control rate (DCR), defined as PR, CR, or stable disease (SD) as assessed by RECIST.
- Progression-free survival (PFS), defined as time from study entry to progression or death, whichever comes first.
- 1-year overall survival (OS) rate, defined by the number of subjects alive 1 year from the time of study entry.
- Safety parameters: Adverse drug reactions and serious adverse drug reactions. Common Terminology Criteria for Adverse Events (CTCAE) version 4.0 will be used.

- Plasma PK parameters will be assessed as shown in the Schedule of Events (Table 8.1)

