## **Adverse Events of Special Concern**

### **Vascular Occlusion**

Arterial and venous thrombosis and occlusions, including fatal myocardial infarction, stroke, stenosis of large arterial vessels of the brain, severe peripheral vascular disease, and the need for urgent revascularization procedures have occurred in at least 27% of ponatinib-treated patients from the phase 1 and phase 2 trials conducted in CML/ALL patient populations (Ponatinib Package Insert, Accessed 4/17/2014). Ponatinib has been associated with fatal and life-threatening vascular occlusion within 2 weeks of starting treatment. Ponatinib has also been associated with recurrent or multi-site vascular occlusion.

In the dose-escalation (phase 1) clinical trial, 48% (31/65) of patients with CML or Ph+ ALL developed vascular occlusive events. The median time to onset of the first vascular occlusion event was 5 months. Ponatinib can cause fatal and life threatening vascular occlusion in patients treated at dose levels as low as 15 mg per day.

Patients with and without cardiovascular risk factors, including patients age 50 years or younger, experienced these events. Vascular occlusion adverse events were more frequent with increasing age and in patients with prior history of ischemia, hypertension, diabetes, or hyperlipidemia (see Table 2.3).

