### **5.7 Follow-up Period**

The follow-up period for a participant begins after the last completed assessment during the active study period. Any participant who discontinued study treatment for any reason other than disease progression, death or withdrawal of consent will continue to have tumor assessments every 12 weeks ( $\pm$ 14 days) until the participant starts another anti-cancer therapy.

All participants should be followed for PFS and survival at least every 3 months ( $\pm$  14 days), up to 2 years after the initial dose of ponatinib.

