- 7 PK samples will be collected pre-dose on Cycle 1 Day 1 and Cycle 2 Day 1. Additional PK samples will be collected on Cycle 1 Day 1 only at the following time-points: 1, 2, and 4 hours ( $\pm$ 10 minutes), and 6 and 8 hrs ( $\pm$ 20 minutes) post dose. Whole blood will be collected in EDTA-K2 tubes (lavender top). Refer to site-specific laboratory manual for further details.
- 8 Disease assessments will initially be performed at 8 week intervals (after cycle 2 [at the beginning of cycle 3 in the table above], after cycle 4 [at the beginning of cycle 5], and so on until cycle 11). From cycle 11 forward, disease assessments will be performed at 12 week intervals (after cycle 13 [at the beginning of cycle 14] and so on). Disease assessments may be limited to the sites of disease. RECIST-defined responses will be confirmed with a repeat assessment in  $\geq$ 4 weeks (See [Section 9](#)). Disease assessments will also be performed at the End of Treatment.
- 9 Any participant who discontinued study treatment for any reason other than disease progression, death or withdrawal of consent will continue to have disease assessments every 12 weeks ( $\pm$ 14 days) until the participant starts another anti-cancer therapy.
- 10 From cycle 11 forward, study visits will be every 6 weeks but disease assessments will be every 12 weeks (after cycle 13, 16, etc).
- 11 Baseline procedures are to be obtained within 14 days of the start of study treatment with the exception of obtaining informed consent and baseline disease assessments, which should be obtained within 28 days prior to the start of study treatment.
- 12 All assessments and procedures (with the exception of baseline) have a  $+$ - 3 day window.

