#### 9.1.1 Definitions

Evaluable for toxicity. All participants who receive at least one dose of study treatment will be evaluable for toxicity from the time of their first treatment.

Evaluable for objective response. Only those participants who have measurable disease present at baseline, have received at least one cycle of therapy, and have had their disease re-evaluated will be considered evaluable for response. These participants will have their response classified according to the definitions stated below. (Note: Participants who exhibit objective disease progression or die prior to the end of cycle 1 will also be considered evaluable.)

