#### **13.3.2 Progression-free survival and 1- year overall survival rate**

Progression free survival (PFS) rates will be calculated from the endpoints described in [Section 9](#). All time-to-event variables will be recorded from the day of study enrollment. For 1-year overall survival (OS) rate, death events will be recorded. One-year OS rate will be defined by the number of participants alive 1 year from the time of study entry.

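### The analysis section takes PFS from Section 9.1.5, which omits death as an event, although Section 1.5 counts progression or death

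*Combined protocol and SAP*

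**What the plan says.** Three places in the protocol bear on PFS.

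- Section 1.5 (Secondary Endpoints): "Progression-free survival (PFS), defined as time from study entry to progression or death, whichever comes first".
- Section 9.1.5: "Progression-Free Survival (PFS) is defined as the duration of time from study entry to time of objective disease progression". Death is not mentioned. The table of contents carries the same sentence.
- Section 13.3.2: "Progression free survival (PFS) rates will be calculated from the endpoints described in" Section 9. It takes the day of enrollment as time zero and mentions recording deaths only for the 1-year overall survival (OS) rate.

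No section says which definition takes precedence, how a death without documented progression enters PFS, or how PFS is censored. Section 9 does provide for early death elsewhere. On evaluability for response, 9.1.1 says: "Participants who exhibit objective disease progression or die prior to the end of cycle 1 will also be considered evaluable". There is no matching provision for PFS.

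For OS, Section 13.3.2 says: "One-year OS rate will be defined by the number of participants alive 1 year from the time of study entry". It gives no denominator and no rule for participants whose status at 1 year is unknown.

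**The concern.** One secondary endpoint has two event definitions, and the analysis section points to the one without death. A participant who dies with no documented progression is an event under 1.5 and not an event under 9.1.5. Section 9.1.5 does not say whether that participant is censored or left out.

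Such deaths are plausible. On the vascular occlusion risk, Section 2.1 states: "Ponatinib has been associated with fatal and life-threatening vascular occlusion within 2 weeks of starting treatment". Footnote 8 to Table 8-1 states: "Disease assessments will initially be performed at 8 week intervals", with the first after cycle 2. A death in the first weeks could therefore precede any on-study scan.

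At stake is the PFS curve, its median and any landmark rate. If deaths are censored, these can only stay the same or look better. An unresolved conflict also leaves the choice of definition open until results are known.

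A smaller, separate point is that a 1-year OS rate described as a count is not fully specified.

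**Working it through.** **Which definition governs.** Section 13.3.2 refers to Section 9. Within Section 9 the only PFS definition is 9.1.5, and it names objective progression alone. An analyst who follows the cross-reference estimates time to progression. Using 1.5 instead means overriding the analysis section.

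**The plan's own figures.** The plan gives no design figure for PFS. Its only operating characteristics are for the primary rule of at least 4 responses in 20 (Section 13.1). By the exact binomial:

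- P(X ≥ 4 | n = 20, p = 0.30) = 0.8929, against the stated 89%.
- P(X ≥ 4 | n = 20, p = 0.10) = 0.1330, against the stated 13%.

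Both reproduce, and neither depends on how PFS is defined.

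**Direction when deaths are censored at the date of death.** The risk sets are the same under both definitions. The Kaplan-Meier product under 1.5 has a factor below 1 at each such death, and under 9.1.5 that factor is absent. The curve under 9.1.5 is therefore never lower, and its median never shorter.

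**Size under the same handling.** The inputs below are assumptions, because the documents supply none of them:

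- f is the share of first events that are deaths without documented progression, set at 5%, 10%, 20% and 30%;
- hazards are constant;
- the true median PFS under 1.5 is 5 months.

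If the hazard for progression or death is λ, the progression-only hazard is (1 − f)λ. Hence:

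- ratio of medians = 1/(1 − f);
- 6-month rate under 1.5 = exp(−ln 2 × 6/5) = 43.5%;
- 6-month rate under 9.1.5 = exp(−ln 2 × (1 − f) × 6/5).

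| f | Ratio of medians | Median read as PFS (true 5 months) | 6-month rate (true 43.5%) |
|---|---|---|---|
| 5% | 1.05 | 5.3 months | 45.4% |
| 10% | 1.11 | 5.6 months | 47.3% |
| 20% | 1.25 | 6.3 months | 51.4% |
| 30% | 1.43 | 7.1 months | 55.9% |

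**Simulation check.** With n = 20, a 24-month cut-off and 20,000 replicates for each f, the ratios of typical Kaplan-Meier medians were 1.05, 1.10, 1.25 and 1.42. The median under 9.1.5 was never the shorter one in 80,000 replicates. The 95% range of the correctly defined median was about 2.6 to 8.8 months, so every shift in the table is smaller than sampling variation at this sample size.

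**OS illustration (assumed counts).** Suppose 10 of 20 participants are known to be alive at 1 year. With all 20 as divisor the rate is 10/20 = 50%. If 1, 2 or 3 have unknown status and are dropped from the divisor, it is 10/19 = 52.6%, 10/18 = 55.6% or 10/17 = 58.8%.

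**The case against.** The strongest reply is that Section 1.5 is the formal endpoint definition and the conventional one. Nothing states that deaths are censored, so a sensible analyst would use 1.5 and this is only an inconsistency. It is an inconsistency, but not a neutral one: 13.3.2 settles the choice by pointing to Section 9. Relying on the analyst to disregard that is not a plan.

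The second reply has force. Section 9.1.5 could also be read as excluding participants who die without progression. Under constant competing hazards the time to first event has the same distribution whichever event comes first, so exclusion gives a true median ratio of 1.00. A simulation with n = 20 and 4,000 replicates for each f moved the typical median by only 2–4%. The median was shorter than the correct one in 7%, 16%, 26% and 33% of replicates for f = 5%, 10%, 20% and 30%. The tabulated ratios and the one-way direction therefore hold only for censoring at death. Exclusion would still not estimate the endpoint in 1.5, since it drops participants according to their outcome.

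Third, the share of such deaths is unknown and may be small. The vascular data come from leukaemia trials. This trial excludes a history of arterial thrombotic disease (3.2.11) and requires thromboprophylaxis and a statin (6.11). It also requires End of Treatment imaging (5.1) and asks for efforts to document progression after treatment stops (9.1.3). All of that stands, and nothing in the documents supports the upper end of the assumed range.

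The contents entry is the same sentence carried forward, not independent evidence. The OS denominator is a missing detail, not a contradiction.

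**Conclusion.** The concern holds. Sections 1.5 and 9.1.5 define different events for PFS, and 13.3.2 sends the calculation to the definition without death. Followed as written, the plan reports time to progression under the name PFS.

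If deaths without progression are censored at death, the bias is zero or upward. Its size rests on an unknown share of such deaths and on constant hazards, and at n = 20 it would not stand out from chance.

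The consequence is limited. Section 13.3 makes secondary endpoints exploratory, no decision depends on PFS, the 4-of-20 rule and its error rates are unaffected, and deaths are still reported as serious adverse events. It should be fixed before analysis because the text prescribes the wrong calculation and the remedy is simple. The OS point is secondary, and this conclusion does not depend on it.

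**What to change.** - **Section 9.1.5 and its contents entry:** adopt the Section 1.5 definition, namely time from study entry to objective progression or death from any cause, whichever is first.
- **Section 13.3.2, PFS:** name the Kaplan-Meier estimator with a confidence interval, and censor participants without an event at their last evaluable disease assessment. State also how PFS is handled when new anti-cancer therapy starts before progression, because Section 5.7 ends scheduled tumor assessments at that point.
- **Section 13.3.2, 1-year OS:** either use Kaplan-Meier with censoring at last contact, or keep a proportion and state the denominator and the handling of unknown status.

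The cost is wording only. Section 5.7 already provides the data: "All participants should be followed for PFS and survival at least every 3 months", up to 2 years after the first dose. The one drawback for the sponsor is that the PFS estimate may be less favourable than under 9.1.5.

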#### **9.1.6 Response Review**

Tumor assessment for RECIST criteria will be performed by independent central review through the DF/HCC Tumor Imaging Metrics Core (TIMC). These reviews will be used only for determining response by RECIST criteria, and do not need to be used for clinical decision making in real time.

For sites outside of DF/HCC, real time clinical decision making will be based upon investigator review of scans. However, copies of required scans (reports plus electronic images on CD) should be sent to the Coordinating Center within 1 week of completion, at which time they will undergo central review through the DF/HCC TIMC. The results of the central review will not be routinely made available to the sites.

### **10 Adverse Event Reporting Requirements**

#### **10.1 Definitions**

##### **10.1.1 Adverse Event (AE)**

An adverse event (AE) is any undesirable sign, symptom or medical condition or experience that develops or worsens in severity after starting the first dose of study treatment or any procedure specified in the protocol, even if the event is not considered to be related to the study.

Abnormal laboratory values or diagnostic test results constitute adverse events only if they induce clinical signs or symptoms or require treatment or further diagnostic tests.

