## **7.2 Dose Delays and Reductions**

Dose delays and/or reductions will be implemented for participants who experience adverse drug reactions as indicated in the following sections.

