### **7.3 Dose Delay and/or Reduction for Adverse Events (AEs) Attributable to the Study Drug**

[Table 7.1](#) describes suggested guidelines for dose modification due to study-drug-related toxicity, graded according to NCI CTCAE 4.0. However, for an individual participant, dose interruptions, reductions and treatment discontinuation should also be based on the clinical circumstance and investigators should use clinical judgment in deciding whether a dose reduction, delay or discontinuation is appropriate for any given clinical circumstance. In general, when the observed toxicity has resolved to  $\leq$  grade 1, the investigator may resume full dosing if clinically indicated.

No dose reduction below 15 mg once daily is permitted for ponatinib. If the participant cannot tolerate a minimum dose of 15 mg per day of ponatinib, despite any allowed interruptions, the participant must be discontinued from study treatment. Doses may be interrupted for study-drug related toxicities for up to 28 days. If a non-hematologic study-drug related toxicity does not resolve to Grade 1 or less after dose interruption for more than 28 days, the participant must be discontinued from study treatment. If a hematologic study-drug related toxicity does not resolve to Grade 1 or less after dose interruption for more than 28 days, the Principal Investigator/Sponsor must be contacted. Additionally, the Principal Investigator/Sponsor must be contacted if any adverse event deemed unrelated to treatment requires dose interruption for more than 28 days. Lastly, for each participant, once a dose reduction has occurred, the dose level may not be re-escalated during subsequent treatment cycles of ponatinib.

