**Table 7.1 Ponatinib: Dose Modifications for Drug Adverse Reactions**

Toxicity	Modification
Nonhematologic Toxicity	
General (Any CTCAE v4.0 nonhematologic toxicity not otherwise specified below)	
Grade 1 or transient Grade 2	No intervention
AST/ALT Elevations	
Grade 1 or transient Grade 2	No intervention
Grade 2 lasting $\geq$ 7 days with optimal care AND total bilirubin $<$ 2 x ULN	Hold ponatinib Resume at 30 mg after recovery to $\leq$ grade 1  Recurrence at 30 mg: Hold ponatinib Resume at 15 mg after recovery to $\leq$ grade 1  Recurrence at 15 mg Discontinue ponatinib
Grade 3 or 4 AND total bilirubin $<$ 2 x ULN	Hold ponatinib Resume at 30 mg after recovery to $\leq$ grade 1  Recurrence at 30 mg Hold ponatinib Resume at 15 mg after recovery to $\leq$ grade 1  Recurrence at 15 mg Discontinue ponatinib
Grade $\geq$ 2 AND total bilirubin $\geq$ 2 x ULN (In the absence of liver metastases)	Discontinue ponatinib
Pancreatitis	
Grade 2 (enzyme elevation or radiologic findings only)	See amylase/lipase section below
Grade 3 (severe pain, vomiting, medical intervention indicated [eg, analgesia, nutritional support])	Hold ponatinib Perform ultrasound or abdominal CT scan with contrast If imaging is positive, continue holding ponatinib and repeat according to clinical care. If imaging is negative, or after resolution by imaging, resume at 15 mg after recovery to $\leq$ grade 1  Recurrence at 15 mg: Repeat above Consider discontinuing ponatinib
Grade 4	Hold ponatinib Consult sponsor
Amylase/Lipase	
Grade $\leq$ 2	No intervention; monitor closely

Toxicity	Modification
Grade 3 with no radiologic findings	Hold ponatinib Resume at 30 mg after recovery to $\leq$ grade 1  Recurrence at 30 mg: Hold ponatinib Resume at 15 mg after recovery to $\leq$ grade 1  Recurrence at 15 mg: Discontinue ponatinib
Grade 3 with radiologic findings or Grade 4	Hold ponatinib Repeat imaging according to clinical care After resolution by imaging, resume at 15 mg after recovery to $\leq$ grade 1  Recurrence at 15 mg: Discontinue ponatinib
LV dysfunction/CHF	
Grade 2 or 3	Hold ponatinib Resume at 30 mg after recovery to $\leq$ grade 1  Recurrence at 30 mg: Hold ponatinib Resume at 15 mg after recovery to $\leq$ grade 1  Recurrence at 15 mg: Discontinue ponatinib
Grade 4	Discontinue ponatinib
Skin rash	

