Grade 2 persistent despite optimal symptomatic therapy	Hold ponatinib Resume at 30 mg after recovery to $\leq$ grade 1  Recurrence at 30 mg: Hold ponatinib Resume at 15 mg after recovery to $\leq$ grade 1  Recurrence at 15 mg: Discontinue ponatinib
Grade 3 persistent despite optimal symptomatic therapy	Hold ponatinib Resume at 30 mg after recovery to $\leq$ grade 1  Recurrence at 30 mg: Hold ponatinib Resume at 15 mg after recovery to $\leq$ grade 1  Recurrence at 15 mg: Discontinue ponatinib

Toxicity	Modification
Hematologic Toxicity	
Drug-Related ANC/platelets	
Grade 1 or 2	No dose adjustment
Grade 3 or 4	Hold ponatinib Resume at 30 mg after recovery to $\leq$ grade 1  Recurrence at 30 mg: Hold ponatinib Resume at 15 mg after recovery to $\leq$ grade 1  Recurrence at 15 mg: Discontinue ponatinib

Definitions: ANC = absolute neutrophil count; CHF = congestive heart failure; CT = computed tomography; LV = left ventricular.

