### **7.5.2 Myelosuppression**

Neutropenia, anemia, and thrombocytopenia have all been commonly reported either together or individually in patients treated with ponatinib. While myelosuppression can occur any time during treatment, its onset most commonly occurs within the first month on treatment. These events can typically be managed with supportive care and, if felt to be treatment related, either a reduction or interruption of treatment with ponatinib should occur (see Table 7.1). Rarely, one or more cytopenias can lead to permanent discontinuation of treatment. The use of hematopoietic growth factors such as granulocyte colony-stimulating factor (G-CSF) or granulocyte-macrophage colony-stimulating factor (GM-CSF) is permitted on study; these agents may be used to support blood counts as clinically indicated to minimize treatment interruptions or repeated dose reductions.

The important clinical adverse event of febrile neutropenia falls under the broad category of myelosuppression. If a patient's individual risk factors place them at high risk of developing febrile neutropenia, primary prophylaxis use of colony-stimulating growth factors for the prevention or reduction of febrile neutropenia is recommended according to the published NCCN guidelines [NCCN Guidelines Version 1.2012 – Myeloid Growth Factors].

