**Table 8-1 Schedule of Events**

Assessment 	Baseline 	Cycle 1		Cycle 2 Day 1	Every 4 weeks (Cycle 3-10)	Every 8 weeks (Cycle 3-10)	Every 6 weeks (Cycle 11+) 	End of Treatment	30 Days After End of Treatment	Follow- up
		Day 1	Day 15							
Informed consent	X									
Demographics	X									
Inclusion / Exclusion Criteria	X									
Medical & Surgical History	X									
Diagnosis & Extent of Tumor	X									
Prior Cancer Therapy	X									
Tumor Mutational Status 	X									
Smoking Status	X									
Vital Signs	X	X	X	X	X		X	X	X	
ECOG Performance Status	X	X	X	X	X		X	X	X	
Physical Exam	X	X		X	X		X	X	X	
Electrocardiogram (ECG) 	X				(X) 		(X) 	X		
Cardiac Imaging (ECHO)	X				(X) 					
Hematology	X	X	X	X	X		X	X	X	
Serum Chemistry	X 	X	X	X 	X		X	X	X	
Pregnancy Test	X							X		
PK Sample		X 		X 						
Concomitant Medications	X	X	X	X	X	X	X	X	X	
Disease Assessment 	X					X	X 	X		X 
Survival										X

Footnotes for Schedule of Events:

- 1 This schedule of events table is meant to provide a convenient display of the timing and scope of required assessments expected at each visit. It is not a comprehensive description of each assessment. A complete list of all study related assessments as well as a detailed description of which is expected can be found in Section 5.
- 2 Tumor mutational status: Any previously identified RET translocation, method of identification, and the dates of identification must be recorded. If available, the presence of additional mutations such as KRAS, EGFR, ALK or ROS should be recorded.
- 3 All ECGs should be 12-lead ECGs. ECGs are to be performed at screening, Cycle 4 Day 1, Cycle 7 Day 1, and Cycle 13 Day 1. Please see [Table 7.1](#) and [Section 7.5](#) for a description of ECG monitoring requirements if a prolonged QTcB develops in the course of the study period.
- 4 An additional echocardiogram may be performed on Cycle 4 Day 1 at the discretion of the Investigator based upon participant symptoms.
- 5 Triglycerides will be collected during the baseline assessment only.
- 6 Chemistries, including serum lipase, should also be drawn on Cycle 2 Day 15.

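### Section 10.1.1 does not count a study-drug hold, reduction or discontinuation as a reason to record a laboratory abnormality as an AE; this is inconsistent with Section 7 and leaves a narrow gap in the AE record

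*Combined protocol and SAP*

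**What the plan says.** Section 10.1.1 states that abnormal laboratory values or test results "constitute adverse events only if they induce clinical signs or symptoms or require treatment or further diagnostic tests". That gives three triggers: signs or symptoms, treatment, and further tests. An action on study drug is not among them.

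Section 7 treats the events that lead to such actions as AEs. Section 7.2 applies dose delays and reductions to "participants who experience adverse drug reactions as indicated in the following sections". Section 7.3 is headed "Dose Delay and/or Reduction for Adverse Events (AEs) Attributable to the Study Drug". Table 7.1 is titled "Ponatinib: Dose Modifications for Drug Adverse Reactions". Two of its rows call for a hold on a laboratory result alone: grade 3 or 4 under "Drug-Related ANC/platelets", and grade 3 or 4 AST/ALT with total bilirubin below 2 x ULN.

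The safety endpoint in Section 1.5 is adverse drug reactions and serious adverse drug reactions, graded by CTCAE 4.0. Section 13.3 makes all secondary endpoints exploratory.

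**The concern.** The same event is an AE under Section 7 and may not be one under Section 10.1.1. A participant could have a grade 3 platelet count, no bleeding and no supportive treatment, have drug held, and recover by the next scheduled visit. A site following Section 10.1.1 to the letter need not enter this on the AE form; a site following Section 7.3 would. Safety and tolerability is a stated objective in Section 1.3, and dose-limiting laboratory changes are part of what a tolerability table should show. At stake is the completeness and consistency across sites of AE-based rates for cytopenias and transaminases.

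**Working it through.** The plan gives no figure on this point to reproduce. The check is a comparison of text, then of the visit calendar.

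**1. Triggers against the dosing rows.** The ANC/platelet row and the grade 3-4 AST/ALT row of Table 7.1 carry no condition on symptoms, treatment or an extra test. Total bilirubin, which the AST/ALT row also needs, is in the routine chemistry panel (Section 5.1, item 11). These rows can therefore lead to a hold without meeting Section 10.1.1. Other rows are less clear: the grade 2 AST/ALT row presupposes optimal care, and the grade 3 amylase/lipase rows turn on radiologic findings, so treatment or imaging may already satisfy the definition.

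**2. Is a hold itself treatment?** The protocol's own usage says not. Section 5.1, item 15 lists what was done with study drug and what treatment was given as separate items to document. The note in Section 10.4.1 separates the need for therapy from a change to existing therapy, but that note governs expedited reporting, not the AE definition.

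**3. Does other text supply the missing trigger?** Sections 10.2 and 10.4.3 cover only what is already an AE. Section 13.3.3 names the CTC criteria but not which laboratory values count. Section 8 and Appendix D, Section 3.10 keep laboratory results as assessments or safety parameters without calling them AEs.

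**4. Can a hold begin and clear on scheduled draws?** Inputs: 28-day cycles (Section 6.3); Table 8-1 with its footnotes, including "Chemistries, including serum lipase, should also be drawn on Cycle 2 Day 15"; and Section 7.3: "Doses may be interrupted for study-drug related toxicities for up to 28 days". Day 1 of cycle k is study day 1 + 28(k - 1). Cycle 1 Day 1 labs are reviewed before the first dose (Section 5.4), so day 1 cannot show a drug effect. Each draw may move by 3 days either way (footnote 12), so a nominal gap g can run from g - 6 to g + 6.

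| Detect-and-clear pair | Nominal gap (days) | With window | Against 28 days |
|---|---|---|---|
| Hematology day 15 to 29 | 14 | 8-20 | always within |
| Hematology day 29 to 57, then every cycle to day 253 | 28 | 22-34 | no margin; can exceed |
| Chemistry day 15 to 29, 29 to 43, 43 to 57 | 14 | 8-20 | always within |
| Chemistry day 57 to 85, then every cycle to day 253 | 28 | 22-34 | no margin; can exceed |
| Cycle 11 onward | 42 | 36-48 | exceeds |

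For hematology, only one pair sits comfortably inside the limit. It falls when the event is most likely: Section 7.5.2 says of myelosuppression that "its onset most commonly occurs within the first month on treatment". From cycle 11, showing recovery within 28 days would normally need an extra draw, which arguably counts as a further test.

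**5. Scale.** One missed participant changes a rate by 1/20 = 5 percentage points. For example, 5/20 = 25% (exact 95% CI 8.7-49.1%) becomes 4/20 = 20% (5.7-43.7%).

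A ceiling can be taken from Table 2.2, on the assumption that its grade 3-4 rates carry over. They come from leukemia patients treated at 45 mg, so they may be too high here.
- Platelets: 20 x 110/449 = 4.90
- Neutrophils: 20 x 61/449 = 2.72
- ALT: 20 x 8/449 = 0.36 (no AST rate is given)

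Platelets and neutrophils together give 7.62 entries, and one participant can contribute to both. This counts all such events, not omitted ones. The documents do not give the share that would be asymptomatic, untreated and not rechecked. Assumed shares of 10%, 25% and 50% would give 0.8, 1.9 and 3.8 entries; nothing below rests on them.

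**6. Primary analysis.** The 4-of-20 rule gives P(X >= 4) = 0.133 at a 10% response rate and 0.893 at 30%, agreeing with the stated 13% and 89%. It counts responses only, so AE recording does not enter.

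**The case against.** The strongest reply is that Section 7 is dosing guidance, which Section 7.3 itself calls suggested, and the inconsistency is built largely from headings. No two passages give opposite instructions about what goes on a form. The protocol also uses toxicity and AE almost interchangeably (Section 5.1, item 15; Appendix D, Section 3.11.1), and the Section 10.4.1 note suggests the drafters regarded laboratory changes that alter therapy as AEs. A sensible site would probably record them.

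The scenario is also demanding. It needs a grade 3-4 result with drug held and no interim count for two weeks or more. Section 6.11 advises withholding thromboprophylaxis below 50,000 platelets and resuming on recovery, which presupposes rechecking; Section 7.5.2 allows growth factors. Either an unscheduled count or supportive treatment would make the event an AE. Missed doses go to the drug-administration eCRF (Section 6.3), a Treatment Form is due on the same schedule as the AE form (Section 11.1.2), and monitoring may cover both AEs and drug administration (Appendix D, Section 5.1). A hold without a matching AE could be queried.

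Most of this stands, and it limits the reach. It does not remove the point. The definition is exclusive, the protocol separates a study-drug action from treatment, and no passage supplies the missing trigger. Monitoring that finds an unmatched hold would still have to apply Section 10.1.1, under which leaving it off the AE form could be defended.

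**Conclusion.** The inconsistency is real and should be corrected, but its consequence is modest. It is clearest for grade 3-4 neutrophil, platelet and AST/ALT events that are asymptomatic, untreated and cleared on a scheduled draw: for hematology chiefly day 15 to day 29, for chemistry the 14-day pairs up to day 57. Later pairs through cycle 10 have no margin once the visit window is applied. The number omitted is unknown and probably small, at 5 percentage points per missed participant for the term concerned. This assumes that sites apply the definition literally and that an unscheduled draw counts as a further test.

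A reader might infer more, and the documents do not support it:
- **That dose-limiting laboratory toxicity is lost to the trial.** Section 8 puts assessment results on the eCRF, so the gap is in the AE record only.
- **That several participants' events will go missing.** The ceiling of about 7.6 entries counts every grade 3-4 platelet and neutrophil event at another trial's rates; no share meeting the narrow conditions is given.
- **That no extra test is ever forced through cycle 10.** A nominal 28-day gap can stretch to 34 days.
- **That the efficacy conclusion is affected.** Response rate, sample size, type I error and power are untouched.

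**What to change.** Reconcile Section 10.1.1 with Section 5.1 item 15, Sections 7.2 and 7.3, Table 7.1 and the Section 10.4.1 note. Add one clause to Section 10.1.1: a laboratory abnormality that leads to interruption, reduction or discontinuation of study drug is recorded as an AE. In Section 13.3.3, state that worst on-treatment CTCAE laboratory grade will be tabulated per participant from the hematology and chemistry values already collected, alongside the AE tables. The table does not depend on how sites read the AE definition.

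The cost is one clause and one table, with slightly more AE entries and somewhat higher reported toxicity rates. No new assessment is needed, no dosing rule changes, and sample size, type I error and power stay as they are.
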